5.4.5 Supportive Secondary PK Endpoints

Samples taken for PK analysis will be processed to plasma and concentrations of AT-511 (free base form of AT-527) and its major metabolites AT-551, AT-229, and AT-273, will be quantified by a validated liquid chromatography-tandem mass spectrometry method.

Descriptive summary statistics for PK concentration data will be provided by visit/sampling time point. Summary statistics will also include geometric mean and coefficient of variation (CV; arithmetic and geometric). Concentrations below lower limit of quantification (LLOQ) will be treated as zero in summary statistics and for PK

parameter calculations. Individual and mean plasma concentration versus time data for AT-511, AT-551, AT-229, and AT-273 will be summarized and plotted.

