6.6 PHARMACOKINETIC ANALYSES

The PK analysis population will consist of patients with sufficient data to enable estimation of key parameters (e.g. maximum concentration [C_{max}] and minimum concentration [C_{min}]).

Samples taken for pharmacokinetic analysis will be processed and concentrations of AT-511 (free base form of AT-527) and its major metabolites will be quantified by a validated liquid chromatography-tandem mass spectrometry method. Descriptive summary statistics for PK concentration data will be provided by visit/sampling time point. Summary statistics will include mean (arithmetic and geometric), SD, coefficient of variation (CV) (arithmetic and geometric), median, minimum, and maximum.

Concentrations below LLOQ will be treated as zero in summary statistics and for PK parameter calculations. Individual and mean plasma concentration versus time data for AT-511, AT-551, AT-229, and AT-273 will be tabulated and plotted.

The following pharmacokinetic parameters will be determined on Day 1: C_{max} , T_{max} after the first dose from the plasma concentration-time data. At steady state on Day 5 the following PK parameters will be determined: $C_{max,ss}$, $T_{max,ss}$ and $C_{trough,ss}$. All PK analysis will be performed using the actual recorded sampling times for AT-511, AT-551, AT-229, and AT-273. Descriptive summary statistics for PK parameters will include mean (arithmetic and geometric), SD, CV (arithmetic and geometric), median, minimum, and maximum. An exception to this is T_{max} where median, minimum, and maximum will be presented. Inter-patient variability and drug accumulation will be evaluated.

Nonlinear mixed effects (NLME) modeling will be used to analyze the dose-concentration-time data of AT-511 and AT-273 in plasma. Population and individual PK parameters (e.g., apparent clearance [CL/F] and apparent steady-state volume of distribution [V_{ss}/F]) will be estimated and the influence of various covariates (e.g., age, gender, and body weight) on these parameters will be investigated. The data collected during this study may be pooled with data collected in other clinical studies (previous Phase I and/or Phase II study in healthy volunteers and patients infected with HCV, COVID-19) as appropriate, to build the population PK model. Secondary PK

parameters may be derived from the individual post-hoc predictions. NLME modeling results will be reported in a standalone document distinct from the clinical study report.

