- Not applicable for a site that has not been granted approval for WGS. Performed only for patients at participating sites who have provided written informed consent to participate. If the sample is not collected at the Day 1 visit for any reason, it may be collected at any later timepoint.
- Study treatment will be administered BID to be taken 12 hours apart for a total of 10 doses. See Section 4.3.2.1 for details.
- Medication (e.g., prescription drugs, over-the-counter drugs, vaccines, herbal or homeopathic remedies, nutritional supplements) and supplemental oxygen used by a patient in addition to protocol-mandated treatment from 7 days (12 months for COVID-19 vaccines) prior to initiation of study drug until the end of study follow-up on Day 33, will be recorded. Any COVID-19 vaccination which has occurred before the patient enrolls into the study or during the study will be recorded in the concomitant medications eCRF, including the product or brand/trade or company manufacturer, if available (examples: Pfizer COVID-19 vaccine, Moderna COVID-19 vaccine) and date administered if known. If not available, report as COVID-19 vaccine.
- After informed consent has been obtained but prior to initiation of study drug, only serious adverse events caused by a protocol-mandated intervention should be reported. After initiation of study drug, all adverse events will be reported until the end of study follow-up telephone call on Day 33.

Appendix 2

Schedule of Pharmacokinetic Samples (for Adults and Adolescents)

Visit	Timepoint	Sample Type
PK sparse sampling ^a		
Day 1 (with reference to 1 st dose)	Predose (-30 min)	RO7496998 (AT-527) PK (plasma)
	1 hour postdose (±30 min)	RO7496998 (AT-527) PK (plasma)
Day 5 (with reference to the morning dose)	Predose (-30 min)	RO7496998 (AT-527) PK (plasma)
	1 hour postdose (±30 min)	RO7496998 (AT-527) PK (plasma)
Day 7	Anytime ^c	RO7496998 (AT-527) PK (plasma)
Optional PK intensive sampling ^b		
Day 1 (with reference to the 1 st dose)	Predose (-30 min)	RO7496998 (AT-527) PK (plasma)
	1 hour postdose (±30 min)	RO7496998 (AT-527) PK (plasma)
	2 hours postdose (±30 min)	RO7496998 (AT-527) PK (plasma)
	4 hours postdose (±30 min)	RO7496998 (AT-527) PK (plasma)
Day 5 (with reference to the morning dose)	Predose (-30 min)	RO7496998 (AT-527) PK (plasma)
	1 hour postdose (±30 min)	RO7496998 (AT-527) PK (plasma)
	2 hours postdose (±30 min)	RO7496998 (AT-527) PK (plasma)
	4 hours postdose (±30 min)	RO7496998 (AT-527) PK (plasma)

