	8 hours postdose (±30 min)	RO7496998 (AT-527) PK (plasma)
Day 7	Anytime ^c	RO7496998 (AT-527) PK (plasma)

PK=pharmacokinetic.

- ^a PK samples to be collected in adult and adolescent patients. Samples can be collected and processed in clinic/at site or at home (if patients consented to home visits).
- ^b Optional PK samples to be collected in adult patients only, and who have consented to PK intensive sampling. Samples to be collected and processed at site only.
- ^c The exact sampling time will be captured in relation to the time of last (10th) dose.

Appendix 3

Temperature

Do not reproduce or distribute. The Sponsor will provide sites with all instruments to be completed in this study.

Temperature:

Please take your temperature now.

What is your temperature right now? (Measure before taking fever medication):

_____ (Choose °C or °F)

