5.7.3 Pharmacokinetic Analyses

The following pharmacokinetic parameters will be determined on Day 1: maximum concentration (C_{max}), time to maximum concentration (T_{max}) after the first dose from the plasma concentration-time data. At steady state on Day 5 the following PK parameters will be determined: $C_{max,ss}$, $T_{max,ss}$, and $C_{trough,ss}$. All PK analysis will be performed using the actual recorded sampling times for AT-511, AT-551, AT-229, and AT-273.

Descriptive summary statistics for PK parameters will include mean (arithmetic and geometric), SD, CV (arithmetic and geometric), median, minimum, and maximum.

An exception to this is T_{max} where median, minimum, and maximum will be presented.

Inter-patient variability and drug accumulation will be evaluated.

Nonlinear mixed effects (NLME) modeling will be used to analyze the dose-concentration-time data of AT-511 and AT-273 in plasma. Population and individual PK parameters (e.g., apparent clearance [CL/F] and apparent steady-state volume of distribution [V_{ss}/F]) will be estimated and the influence of various covariates (e.g., age, sex, and weight) on these parameters will be investigated. The data collected during this study may be pooled with data collected in other clinical studies (previous Phase I and/or Phase II study in healthy volunteers and patients infected with hepatitis C virus [HCV], COVID-19) as appropriate, to build the population PK model. Secondary PK parameters may be derived from the individual post-hoc predictions. NLME modeling results will be reported in a standalone document distinct from the clinical study report.

Additional PK analyses may be conducted as appropriate. The PK data and parameters derived from these analyses may be used for exploratory graphical analyses of the PD data and parameters.

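### PK concentrations below LLOQ are set to zero in statistics that include the geometric mean and geometric CV, which then become zero and undefined respectively

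*SAP*

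**What the plan says.** SAP 5.4.5 covers the plasma concentrations of AT-511 and its three metabolites, a stated secondary endpoint. On the statistics to be tabulated by visit and sampling time it says: "Summary statistics will also include geometric mean and coefficient of variation", and specifies both the arithmetic and the geometric form of the CV. The next sentence gives the rule for low values: "Concentrations below lower limit of quantification (LLOQ) will be treated as zero in summary statistics". It extends that rule to PK parameter calculations.

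Protocol 6.6 also asks for arithmetic and geometric means and CVs of concentrations, and says: "Concentrations below LLOQ will be treated as zero in summary statistics and for PK parameter calculations".

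SAP 5.7.3 covers the parameters (Cmax, Tmax, and Ctrough at steady state): "Descriptive summary statistics for PK parameters will include mean (arithmetic and geometric), SD, CV (arithmetic and geometric), median, minimum, and maximum". Only Tmax is excepted; it gets median, minimum and maximum.

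Neither document exempts the geometric statistics from the zero rule, says that zeros are left out of them, or sets a proportion below LLOQ beyond which they are not reported. By contrast, SAP 5.1 gives viral RNA a non-zero value before the log10 transform: 119 copies/mL for a positive sample below the limit of 120, and 60 copies/mL (half the limit) for a negative one.

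**The concern.** A geometric mean is the exponential of the average log, and a geometric CV is a function of the variance of the logs. Zero has no logarithm. A rule that puts zeros into these statistics therefore defeats them, and the plan requires both the rule and the statistics.

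The rule will be triggered. Day 1 predose is sampled in both the sparse and the intensive schedule (Protocol Appendix 2), before any study drug, so values below LLOQ are expected there by design. They are plausible at Day 7, which may be taken at any time that day: "The exact sampling time will be captured in relation to the time of last (10th) dose". They are possible at the Day 5 predose sample, from which trough is read.

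At stake is whether the geometric columns of the PK tables can be produced as specified. If they cannot, someone will have to choose a convention after the data are in. Depending on that choice, the arithmetic and geometric means in one table could rest on different patients.

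**Working it through.** The documents give no figure on this point to reproduce, and no PK LLOQ, no expected fraction below LLOQ and no between-patient variability. The failure of the rule needs none of these. The size of any bias does, so those inputs are assumed below.

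**Step 1: the rule as written.** Take ten illustrative values, one of them below LLOQ and set to zero: 0, 5, 8, 10, 12, 15, 20, 25, 30, 40.

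| Statistic | Zero kept (as written) | Zero dropped |
|---|---|---|
| Arithmetic mean | 16.5 | 18.3 |
| Arithmetic CV | 74.5% | 62.7% |
| Geometric mean, (product)^(1/n) | 0 | 15.2 |
| Geometric CV, sqrt(exp(var of logs) − 1) | undefined | 75.4% |

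If all ten values are zero, as expected at Day 1 predose, the geometric mean is 0, the geometric CV is undefined and the arithmetic CV is 0/0.

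**Step 2: how easily it is triggered.** One value is enough. With 1386 patients randomized 2:1, about 1386 × 2/3 = 924 are on active drug; Protocol 4.2.2 says placebo samples are not assayed by default. If all 924 are sampled at a post-dose time point, the chance of at least one value below LLOQ is 1 − (1 − f)^924. That is about 60% at an assumed f = 0.1% and over 99.9% at f = 1%.

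**Step 3: if zeros are dropped from the geometric statistics (assumed).** For lognormal data with log SD s and a fraction q below LLOQ, let z be the q-quantile of the standard normal, φ its density and λ = φ(z)/(1 − q).

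- Geometric mean relative to truth = exp(sλ).
- Log variance after dropping = s²(1 + zλ − λ²).

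At q = 10%, z = −1.2816 and λ = 0.1755/0.9 = 0.195. With s = 0.5, exp(0.0975) = 1.10; with s = 1.0, exp(0.195) = 1.22.

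| Assumed fraction below LLOQ | Geometric mean too high by (s = 0.5 to 1.0) |
|---|---|
| 10% | 10% to 22% |
| 20% | 19% to 42% |
| 40% | 38% to 90% |

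For the CV, assume true geometric CVs of 50% and 100%, using s = sqrt(ln(1 + CV²)), which gives 0.472 and 0.833. For 50% at q = 10%, the log variance is 0.223 × (1 − 0.250 − 0.038) = 0.159, so the geometric CV becomes sqrt(exp(0.159) − 1) = 42%.

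| Assumed fraction below LLOQ | True 50% becomes | True 100% becomes |
|---|---|---|
| 5% | 45% | 87% |
| 10% | 42% | 80% |
| 20% | 37% | 71% |

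**Step 4: arithmetic CV with zeros kept.** It can be computed but is inflated. At 5%, 10% and 20% below LLOQ, a true 50% becomes 54%, 58% and 68%; a true 100% becomes 101%, 103% and 109%.

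**Step 5: substituting LLOQ/2.** With L = exp(sz), the LLOQ relative to the true geometric mean, the ratio to truth is exp(q·ln(L/2) + (1 − q)·sλ).

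| Assumed fraction below LLOQ | Ratio, true CV 50% | Ratio, true CV 100% |
|---|---|---|
| 5% | 0.98 | 0.98 |
| 10% | 0.95 | 0.97 |
| 20% | 0.92 | 0.96 |
| 50% | 0.85 | 0.99 |

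Up to 20% below LLOQ the geometric mean is about 2% to 8% low. Under the same two CVs, dropping the zeros makes it 5% to 34% high.

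**The case against.** The best case against the point is that it is small and partly conjectural.

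- The PK analysis is labelled supportive and is descriptive. Median, minimum and maximum are also tabulated and individual concentrations are plotted. With fewer than half the values below LLOQ, the zero rule does not move the median. AT-511 and AT-273 are also modelled by nonlinear mixed effects in a separate report. All of this stands.
- A geometric mean of zero is conspicuous and would mislead nobody. Table specifications sit in a separate document (SAP section 1), which may say when a statistic is not calculated. That is possible but not shown, and it would not alter the SAP's own instruction.
- At Day 1 predose, the one time point where values below LLOQ are expected by design, zero is appropriate and a geometric mean has no interpretive value. This stands and shapes the fix.
- LLOQ/2 and any reporting cutoff are conventions among several. This also stands.

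A reader might infer more than the documents support. One inference is that every CV fails: the arithmetic CV does not, unless all values are zero. Another is that dropping zeros inflates the CV: the geometric CV falls. A third is that the reported geometric means will be too high: neither document says zeros are dropped, and no LLOQ or below-LLOQ rate is given, so the percentages are illustrations. Nor do the documents show that trough or Day 7 values will often be below LLOQ. Cmax is unlikely to be affected.

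**Conclusion.** The point holds for the geometric mean and geometric CV. It is a stated rule that fails when applied rather than a missing detail: at any time point with one value below LLOQ, and for trough if one patient's trough is below LLOQ, the required geometric mean is 0 and the geometric CV does not exist. This part rests on no assumption.

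The bias is conditional. It needs an analyst to drop zeros, lognormal data, and assumed values for the log SD and the fraction below LLOQ. On those terms the geometric mean is 10% to 22% high at 10% below LLOQ, and the geometric CV is low.

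The consequence is minor. It is confined to descriptive PK tables; no efficacy test, significance level or sample size depends on it. It is worth repairing because the repair is cheap and avoids choosing a convention after the data are seen.

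**What to change.** Amend SAP 5.4.5 and 5.7.3, and record the departure from Protocol 6.6 in SAP Appendix 1:

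- Keep zero for arithmetic summaries and for Day 1 predose. Report the geometric statistics at Day 1 predose as not calculated.
- For the geometric mean and geometric CV of post-dose concentrations and of Ctrough at steady state, substitute LLOQ/2. This follows the SAP's own approach to viral RNA, which also avoids zeros before taking logs. State explicitly that the substitution covers trough.
- Show the number of values below LLOQ at each time point.
- Report geometric statistics as not calculated above a pre-specified proportion below LLOQ, for example one half, and label that cutoff as a convention.

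The cost is a few SAP sentences, an Appendix 1 entry and one extra count in the tables. The change can be made in the SAP alone. Two downsides should be accepted openly: arithmetic and geometric summaries will use different substituted values for the same samples, and LLOQ/2 leaves a small bias, about 2% to 8% low at an assumed 5% to 20% below LLOQ.

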5.5 EXPLORATORY ENDPOINT(S) ANALYSIS

5.5.1 Exploratory Efficacy Endpoints

- Proportion of patients with ≥ 1 COVID-19-related medically attended visit (handling missing data due to study withdrawal or loss of follow up with multiple imputation)
- Proportion of patients requiring hospitalizations for COVID-19 (handling missing data due to study withdrawal or loss of follow up with multiple imputation)
- Frequency (Proportion) of medically confirmed COVID-19-related complications (handling missing data due to study withdrawal or loss of follow up with multiple imputation)

5.5.2 Exploratory Virology Endpoints

The exploratory virology endpoints for this study are as follows:

- Treatment-emergent amino acid substitutions in SARS-CoV-2 viral genes (such as *nsp12* and potentially other genes)
- Anti-SARS-CoV-2 antibody status/titer for neutralizing antibodies and anti-S antibodies at specified timepoints
- Change from baseline in amount of SARS-CoV-2 virus titer at each timepoint
- Time to cessation of SARS-CoV-2 viral shedding as measured by virus titer
- Proportion of patients with positive SARS-CoV-2 virus titer at specified timepoints
- AUC of SARS-CoV-2 virus titer
- Drug susceptibility in patients with evaluable virus at specified timepoints

Time to event, incidence, proportion and change from baseline endpoints will be analyzed using the same approach as described for secondary virology endpoints in Section 5.1.

Additional analyses adjusting by baseline amount of virus RNA may also be conducted. Other virology endpoints will be summarized descriptively.

5.5.3 Exploratory Patient Reported Outcome and Health Utility Endpoints

Data from the PGIS and EQ-5D-5L will be used in separate analysis to inform understanding of the COVID-19 Symptom Diary and health utilities. The patient reported outcomes and health utility endpoints for this study are as follows:

- Patient's global impression of severity (PGIS) of COVID-19 symptoms as assessed through the use of the PGIS at Day 14 and Day 29
- Change from baseline in EQ-5D-5L health utility index-based and Visual Analog Scale (VAS) scores at specified timepoints

The EuroQol 5-Dimension 5-Level (EQ-5D-5L) will be scored according to its manual, and results will be reported separately from the clinical study report.

Patient-reported outcomes (PRO) and health utility endpoints will be summarized descriptively.

5.6 OTHER SAFETY ANALYSES

5.6.1 Extent of Exposure

The number of administrations and the duration of exposure to study treatment will be summarized using descriptive statistics. The duration of exposure will be calculated in days as the date and time of last dose of study treatment minus the date and time of first dose of study treatment plus 12 hours and divided by 24 to convert to days.

5.6.2 Adverse Events

Separate summaries will be generated for SAEs, deaths, adverse events leading to discontinuation of study treatment, adverse events leading to discontinuation of study, adverse events of special interest, SAEs suspected to be caused by study treatment and adverse events suspected to be caused by study treatment, as assessed by the investigator. In addition, adverse events and SAEs by time of onset according to the following categories will be reported: Days 1-7, Days 8-14, and Days ≥ 15 . If a low number of events is observed, a listing may be produced in place of a summary table. Adverse events will also be listed.

Adverse events of special interest for this study will be identified by the relevant checkbox on the eCRF and are as follows:

- Cases of potential drug induced liver injury that include an elevated alanine aminotransferase (ALT) or aspartate aminotransferase (AST) in combination with either an elevated bilirubin or clinical jaundice, as defined by Hy's Law (see Protocol Section 5.3.5.6)
- Suspected transmission of an infectious agent by the study drug, as defined below
 - Any organism, virus, or infectious particle (e.g., prion protein transmitting transmissible spongiform encephalopathy), pathogenic or non-pathogenic, is considered an infectious agent. A transmission of an infectious agent may be suspected from clinical symptoms or laboratory findings that indicate an infection in a patient exposed to a medicinal product. This term applies only when a contamination of the study drug is suspected.

Additional safety analyses for adverse event and SAEs divided by age and vaccination status subgroup will also be produced.

5.6.3 Laboratory Data

Summaries of the number of patients by NCI CTCAE v5.0 grade for hematology (white blood cells [WBC], hemoglobin, platelets), and for chemistry (alkaline phosphatase, ALT,

AST, total bilirubin, creatinine), and renal function will be produced. The number of patients will be summarized by NCI CTCAE grade category for baseline and worst post baseline value.

Patients with values outside the reference will be listed, with an indication of the direction of the abnormality (high, low).

A listing of patients who meet the pre-specified criteria shown in [Table 5](#) during the study will be presented for each treatment group.

Table 5 Pre-specified Treatment-Emergent Abnormal Laboratory Criteria

AST (U/L) or ALT (U/L) and Total bilirubin (mg/dL)
AST (U/L) or ALT (U/L) $> 3 \times$ Baseline
AST (U/L) or ALT (U/L) $> 5 \times$ Baseline
AST (U/L) or ALT (U/L) $> 3 \times$ Baseline in combination with total bilirubin (mg/dL) $> 2 \cdot ULN$

ALT= alanine aminotransferase; AST= aspartate aminotransferase; ULN= upper limit of normal.

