- Abnormal laboratory test results at screening, defined as meeting any of the following sets of criteria:
 - ALT or AST > 5 × upper limit of normal (ULN)
 - Total bilirubin > 1.5 × ULN, unless the patient has known Gilbert disease
 - Creatinine clearance < 60 mL/min
 - Total WBC < 2,500/mm³ or ANC < 800/mm³
 - Platelet count < 80/mm³

Local laboratory test results from standard-of-care tests performed prior to obtaining written informed consent and ≤ 48 hours before randomization may be used; such tests do not need to be repeated for screening.

- Requirement of any prohibited medications during the study
- *Other known active viral or bacterial infection at the time of screening, such as influenza*
Note: This exclusion does not apply to patients with stable chronic viral infections, such as chronic HCV or HIV providing other eligibility criteria are met.
- Any clinically significant medical condition or laboratory abnormality that, in the opinion of the investigator, could jeopardize the safety of the patient or affect patient compliance or safety/efficacy observations during the study
- *COVID-19 vaccination within ≤40-days prior to enrollment (second dose if applicable)*

End of Study

The end of this study is defined as the date when the last patient, last visit (i.e., safety follow-up telephone call), occurs or the date at which the last data point required for statistical analysis or safety follow-up is received from the last patient, whichever occurs later. The end of the study is expected to occur approximately 33 days after the last patient has been enrolled.

In addition, the Sponsor may decide to terminate the study at any time.

Length of Study

The total length of the study, from screening of the first patient to the end of the study, is expected to be approximately 6 months.

Investigational Medicinal Products

The investigational medicinal product for this study is RO7496998 (AT-527) or matching placebo.

Test Product (Investigational Drug)

For patients randomized to receive study drug, RO7496998 (AT-527) will be provided as 275 mg tablets; two tablets will be administered orally BID from Day 1 to Day 5.

Comparator

For patients randomized to receive placebo, placebo will be provided as 275 mg tablets; two tablets will be administered orally BID from Day 1 to Day 5.

Statistical Methods

Primary Analysis

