4.1.2 Exclusion Criteria

Patients who meet any of the following criteria will be excluded from study entry:

- Clinical signs indicative of COVID-19 illness requiring hospitalization defined as any of the following:
 - In adults: respiratory rate \geq 30, heart rate \geq 125 bpm, SpO₂ \leq 93% on room air
 - In adolescents: respiratory rate \geq 30, heart rate \geq 130 bpm, SpO₂ \leq 93% on room air
- Admitted to a hospital prior to randomization or is hospitalized (inpatient) at randomization due to COVID-19

Note: If local policy requires COVID-19 isolation or internment in a hospital or similar facility, such as in Japan, but those patients otherwise meet the inclusion criteria, this exclusion may not apply.

- In the opinion of the investigator, is likely to experience imminent deterioration and require hospitalization
- Treatment with an investigational drug within 5 half-lives or 3 months (whichever is longer) of randomization
- Treatment with a COVID-19 therapeutic agent including, but not limited to, other direct or indirect acting antivirals *against SARS-CoV-2 (such as remdesivir or favipiravir), systemic or inhaled steroids (such as dexamethasone or inhaled budesonide), colchicine, ivermectin, interferons, convalescent plasma, monoclonal antibodies against SARS CoV-2 or interleukin 6 (IL-6), intravenous immunoglobulin or other EUA-approved treatments within 3 months or less than 5 drug elimination half-lives (whichever is longer) prior to the screening visit*
- Concomitant use of P-glycoprotein (P-gp) inhibitors or inducers listed in Section 4.4.3
- Known allergy or hypersensitivity to components of study drug
- Pregnant or breastfeeding, or intending to become pregnant during the study or within 30 days after the final dose of RO7496998 (AT-527)

Women of childbearing potential must have a negative pregnancy test result at screening prior to initiation of study drug.

- Abnormal laboratory test results at screening, defined as meeting any of the following sets of criteria:
 - ALT or AST $>5 \times$ upper limit of normal (ULN)
 - Total bilirubin $>1.5 \times$ ULN, unless the patient has known Gilbert disease
 - Creatinine clearance $<60 \text{ mL/min}$
 - Total WBC $<2,500/\text{mm}^3$ or ANC $<800/\text{mm}^3$
 - Platelet count $<80/\text{mm}^3$

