5.2.3 Adverse Events of Special Interest (Immediately Reportable to the Sponsor)

Adverse events of special interest are required to be reported by the investigator to the Sponsor immediately (i.e., no more than 24 hours after learning of the event; see Section [5.4.2](#) for reporting instructions). Adverse events of special interest for this study are as follows:

- Cases of potential drug-induced liver injury that include an elevated ALT or AST in combination with either an elevated bilirubin or clinical jaundice, as defined by Hy's Law (see Section [5.3.5.6](#))
- Suspected transmission of an infectious agent by the study drug, as defined below

Any organism, virus, or infectious particle (e.g., prion protein transmitting transmissible spongiform encephalopathy), pathogenic or non-pathogenic, is considered an infectious agent. A transmission of an infectious agent may be suspected from clinical symptoms or laboratory findings that indicate an infection in a patient exposed to a medicinal product. This term applies only when a contamination of the study drug is suspected.

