5.3.5.6 Abnormal Liver Function Tests

The finding of an elevated ALT or AST ($>3 \times$ baseline value) in combination with either an elevated total bilirubin ($>2 \times$ ULN) or clinical jaundice in the absence of cholestasis or other causes of hyperbilirubinemia is considered to be an indicator of severe liver injury (as defined by Hy's Law). Therefore, investigators must report as an adverse event the occurrence of either of the following:

- Treatment-emergent ALT or AST $>3 \times$ baseline value in combination with total bilirubin $>2 \times$ ULN (of which $\geq 35\%$ is direct bilirubin)
- Treatment-emergent ALT or AST $>3 \times$ baseline value in combination with clinical jaundice

The most appropriate diagnosis or (if a diagnosis cannot be established) the abnormal laboratory values should be recorded on the Adverse Event eCRF (see Section 5.3.5.1) and reported to the Sponsor immediately (i.e., no more than 24 hours after learning of the event), either as a serious adverse event or an adverse event of special interest (see Section 5.4.2).

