5.4.4.4 Change from Baseline in Targeted Laboratory Results

Laboratory data will use ranges from local laboratories and laboratory values will be converted to Système International units.

Summary tables will present the observed and change from baseline values of the laboratory chemistry parameters: alanine aminotransferase, aspartate aminotransferase, alkaline phosphatase, total bilirubin, blood urea nitrogen, creatine kinase, lactate dehydrogenase, C-reactive protein and creatinine, and laboratory hematology parameters: hemoglobin, white blood cell count, and platelets, and laboratory coagulation parameter: D-dimer for baseline and Day 5 visits by treatment group.

For laboratory results, time windows for unscheduled and early termination visits are given in [Table 4](#) below. Where multiple measurements within a visit window are available for a patient, the value obtained closest to the target timepoint (center of the acceptable time window) will be used.

Table 4 Laboratory Time Windows

Scheduled Timepoint	Acceptable Time Window
Baseline (Day 1 pre-dose)	Day 1 pre-dose
Day 5	Day 4 – Day 6

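### SAP Table 5 and Protocol 5.3.5.6 scale ALT/AST only to the patient's own baseline, so a patient entering at the permitted 5×ULN meets the combined liver criterion only above 15×ULN

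*SAP*

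**What the plan says.** **Entry.** The protocol synopsis and section 4.1.2 exclude patients with "ALT or AST > 5 × upper limit of normal (ULN"), so a value of exactly 5×ULN is admissible. Total bilirubin above 1.5×ULN is also excluded, except in known Gilbert disease.

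**Special-interest event.** Protocol 5.2.3 names "Cases of potential drug-induced liver injury that include an elevated ALT or AST in combination with either an elevated bilirubin or clinical jaundice" and sends the reader to 5.3.5.6 for the definition. That section gives two criteria, and both start from ALT or AST above 3×baseline. One adds total bilirubin above 2×ULN, at least 35% of it direct. The other ends "baseline value in combination with clinical jaundice". SAP 5.6.2 refers back to the same protocol section and identifies these events by an eCRF checkbox.

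**Listing.** SAP 5.6.3, Table 5, has three rows for ALT or AST: above 3×baseline, above 5×baseline, and above 3× "Baseline in combination with total bilirubin (mg/dL") above 2×ULN. None expresses ALT or AST in ULN.

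**Baseline.** SAP 5.1 takes the last value before first dose. SAP Table 4 labels the laboratory baseline "Baseline (Day 1 pre-dose"), while Protocol Appendix 1 schedules the pre-treatment safety laboratory tests at screening.

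**The concern.** The entry limit and the bilirubin limb are fixed on the ULN scale, but the ALT/AST limb moves with each patient's starting value. The same criterion therefore asks for very different absolute values in different patients. It asks for the largest values from patients who enter with raised enzymes. Such patients are foreseeable: Protocol 3.3.2 counts chronic liver disease as a risk factor, and Protocol 4.1.2 admits stable chronic HCV.

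Liver injury is one of only two special-interest events, and the protocol cites liver damage as a known problem with some nucleoside analogues. The SAP's laboratory change tables cover baseline and Day 5 only. Later values would come from early-termination or unscheduled visits. A pre-specified paired listing on the ULN scale would make the hepatic data easier to read for these patients, and the plan does not have one.

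**Working it through.** **Inputs**
- Highest admissible ALT/AST at entry: 5×ULN (Protocol 4.1.2).
- Criterion multiples: 3 and 5 times baseline (SAP Table 5); 3 times baseline (Protocol 5.3.5.6).
- Bilirubin limb: above 2×ULN (both documents).
- Highest admissible bilirubin at entry outside Gilbert disease: 1.5×ULN (Protocol 4.1.2).
- Distribution of baseline ALT/AST: not given. Every baseline below except 5×ULN is illustrative.

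**Formula.** Threshold in ULN = criterion multiple × (baseline ÷ ULN). The documents state no such threshold, so there is no planned figure to reproduce.

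| Baseline (×ULN) | >3×baseline is met above | >5×baseline is met above |
|---|---|---|
| 0.3 (assumed) | 0.9×ULN | 1.5×ULN |
| 0.5 (assumed) | 1.5×ULN | 2.5×ULN |
| 1 | 3×ULN | 5×ULN |
| 2 | 6×ULN | 10×ULN |
| 5 (entry limit) | 15×ULN | 25×ULN |

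**High end.** Take a patient who enters at 5×ULN and reaches 12×ULN with bilirubin 3×ULN. The ratio to baseline is 12 ÷ 5 = 2.4, below 3. The patient meets no Table 5 row and neither criterion in Protocol 5.3.5.6. At 14×ULN the ratio is 14 ÷ 5 = 2.8 and the answer is the same. Outside Gilbert disease this patient's bilirubin was at most 1.5×ULN at screening, so it has at least doubled (3 ÷ 1.5 = 2).

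**Low end.** The >3×baseline row is met inside the normal range when 3 × baseline is below 1×ULN, that is, when baseline is below one third of ULN. At 0.3×ULN it is met at just over 0.9×ULN.

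**Crossover.** The two scales agree at a baseline of 1×ULN. Above it, the baseline multiple needs a higher absolute value than the same multiple of ULN; below it, a lower one.

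**Other planned outputs.** SAP 5.6.3 lists all values outside the reference range and tabulates CTCAE grade at baseline and at worst post-baseline, including ALT, AST and total bilirubin. Protocol 5.3.5.4 lets an investigator report any laboratory value judged clinically significant. None of these is a criterion that pairs ALT/AST in ULN with bilirubin. The special-interest summary in SAP 5.6.2 does pair the two, but through Protocol 5.3.5.6 and hence through the same baseline multiple.

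**The case against.** The SAP follows the protocol here. Table 5 is a list of treatment-emergent criteria, and change from baseline is a coherent measure when some patients enter with raised enzymes. Nothing in the documents requires a ULN scale. That stands: this is a gap in what the plan will show, not a computational error or a departure of the SAP from the protocol. The added rows would sit beside the existing ones, so nothing is lost.

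Four stronger readings are tempting, and the documents do not support them.

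- *Such a patient goes unseen.* No. The 12×ULN and 3×ULN values would both qualify for the out-of-range listing, be graded in the CTCAE summary, and be reportable on investigator judgment. Whether the listing shows them together cannot be told, because SAP section 1 puts listing layouts in a separate document.
- *Table 5 is the only output pairing transaminases with bilirubin, so the hepatic conclusion rests on the wrong patients.* No. The special-interest summary pairs them too, and hepatic safety also draws on change-from-baseline tables, adverse event summaries and iDMC review. Table 5 is descriptive and drives no test.
- *Protocol 5.2.3 contradicts 5.3.5.6 by asking for an elevated ALT or AST.* Section 5.3.5.6 itself attaches >3×baseline to that word, so one section defines the other. What remains is that the definition does not guarantee a value above normal. A low-baseline patient would still need the bilirubin or jaundice limb to become a special-interest event; only the simple listing row is met on ALT or AST alone.
- *Table 4 sets a rival baseline.* Its windows are introduced for unscheduled and early-termination visits, and SAP 5.1 already defines baseline. The label is loose but not a second rule.

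**Conclusion.** The point holds in a limited form. ALT/AST enters the liver-injury criteria only as a multiple of baseline, while entry allows up to 5×ULN. At that limit the combined criterion is met only above 15×ULN, whatever the bilirubin. At an assumed baseline of 0.3×ULN, the simple row is met at just over 0.9×ULN.

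The 15×ULN figure follows directly from the documents and is the worst case. How many patients would be affected is unknown, since no baseline ALT/AST distribution is given. The low-end figure depends on the assumed baseline. A reader might infer that liver cases would be lost to the trial. The documents do not support that; they support only the absence of a planned ULN-based criterion pairing ALT/AST with bilirubin. It is a worthwhile, inexpensive improvement to the SAP.

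**What to change.** In SAP Table 5, keep the three existing rows and add listing rows for:
- ALT or AST >3×ULN;
- ALT or AST >5×ULN;
- ALT or AST >3×ULN with total bilirubin >2×ULN.

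Show baseline ALT, AST and total bilirubin in measured units and in multiples of ULN beside each listed patient. In Table 4, replace the Day 1 label with the SAP 5.1 definition, which will normally mean the screening value.

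The entry limit (synopsis and Protocol 4.1.2), the special-interest wording (5.2.3), the reporting criteria (5.3.5.6) and SAP Table 5 should be read together and reconciled. That includes the direct-bilirubin condition and the jaundice criterion, which Table 5 does not carry. The reporting rule itself is for the sponsor to decide.

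**Cost.** A few listing rows and baseline columns, from data already planned and local ranges already used under SAP 5.4.4.4; no new sampling. The downside is that some listed patients will have elevations that pre-date treatment: anyone entering above 3×ULN and staying there meets the first added row. The baseline columns identify them. The combined row is less exposed, because its bilirubin limit of 2×ULN lies above the 1.5×ULN entry limit, outside Gilbert disease.
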